Take your sexuality back - a feasibility study of a new intervention for sexually traumatized women

Our goal of this PhD project is to establish a scientific foundation for a novel group-based treatment intervention to rehabilitate the sexuality of women who have experienced sexual trauma. There is an urgent need to gather insights into the experiences of participants and their partners in order to identify necessary improvements, evaluate the intervention's potential efficacy and gain a more comprehensive understanding of treatment outcomes before initiating a larger randomized controlled trial, and implementing the intervention in the healthcare system. We will obtain data from interviews with group participants and their partners, as well as from measurements taken before, after, and at follow-up. This feasibility study has the potential to improve the quality of health services, and benefit patients in specialist healthcare, sexually traumatized women and their partners in general, and the research community. Our research group has extensive experience and expertise in this field, and the project aligns with the research strategies of both STHF and HSØ.

1. Scientific background and significance

Traumatized sexuality is a significant women's health issue. According to a Norwegian study from 2023, 1 in 5 women report being subjected to rape by force or coercion, rape during sleep, or both (1). The risk of developing Post-Traumatic Stress Disorder (PTSD) following sexual abuse is higher than that associated with other types of traumas (2, 3), underscoring the severe impact on victims. Sexual abuse, characterized by violations of personal boundaries, can profoundly affect individual's relationship with their body and sexuality (4, 5). Common sexual symptoms post-trauma include dissociation or intrusive memories during sexual activity, shame and guilt concerning the body and sexuality, a perceived obligation to satisfy the partner's needs, engagement in high-risk sexual behaviors, relational difficulties, and sexual dysfunctions (4, 6, 7). For many abused women, intimacy with a partner is so closely associated with pain and trauma that it leads to dysfunctional relational patterns and sexual challenges within a partnership (8, 9).

Traditional approaches to trauma treatment have shown minimal improvement in sexual dysfunctions after abuse (10). Researchers and advocacy groups have emphasized the necessity of integrating a focus on intimacy and sexuality within psychological therapies to facilitate the rehabilitation of clients' sexual health and to include eventual partners in the process (8, 11-14). A growing body of research underscores that sexual shame plays a critical role in maintaining sexual dysfunctions, prompting researchers and clinicians to call for interventions that can resolve sexual shame (15-17). Group therapy has been suggested as a particularly effective intervention for targeting sexual shame, creating a space where it is possible to talk about both natural and traumatized sexuality, normalizing sexual trauma symptoms, and enabling connection with others in similar situations (13, 15, 18).

Gewirtz-Meydan's review of empirical research on the treatment of sexual dysfunctions after sexual abuse identified six therapeutic approaches (13). Only one of them was designed for use in a group setting; however, it was only tested and validated on a non-clinical population, included only two group sessions, relied on participants practicing on their own and did not involve partners (13, 19). This highlights a significant gap in evidence-based practices that integrate trauma-focused and sex therapy techniques for treating survivors of sexual trauma in a clinical population of patients with high symptom pressure (10, 13, 20). Consequently, to be able to respond to the needs of the large number of sexually traumatized women referred to Telemark Hospital Trust (STHF), we developed a new group-based intervention named "Take Your Sexuality Back" (TYSB), tailored to the needs of these women. Many of them had experienced long-term complex childhood traumas and had profound sexual post-traumatic symptoms that prevented them from experiencing intimacy as something positive.

We designed the TYSB intervention to be trauma-sensitive, focusing on traumatized sexuality and incorporating regulatory skills to prevent re-traumatization when addressing sex-positive themes, thus accommodating a wide range of trauma-related symptoms, sexual shame, sexual dysfunctions, and regulation difficulties (21-24).

We have continually evaluated and developed TYSB since 2019. A collaboration between the Norwegian Women's Sanitary Association (NKS) and STHF resulted in a psychoeducational book (23) and dissemination of knowledge about traumatized sexuality across women's health centers nationwide (25). The TYSB intervention consists of 12 weekly sessions (2.5 hours each) and a half-hour video session with repetition of exercises two days after each session. The treatment integrates psychoeducation, exercises, reflections, and sharing in a group (table 1). Examples of exercises include strengthening personal boundaries, self-regulation, awakening the senses, handling triggers, body awareness, and reflecting on sexual schemas. In sessions 4 and 10, we invite partners to participate. Participants without partners also join these sessions to gain valuable rehearsal and insight into how to communicate with a future partner.

Textbox 1: Overview of central themes covered in the TYSB intervention

Session	Theme	Session	Theme
1	The history of sexuality How to rebuild personal boundaries	7	Sexual arousal patterns and fantasies. The dynamics of change processes.
2	Reflecting over one's own sexual history. Strengthening self-compassion and selfcare	8	Relationships, communication skills and steps to overcome fear of intimacy.
3	Common aftereffects of sexual trauma. Sexual shame and self-regulation.	9	Ways to restart couple sexuality. Building sexual intimacy step by step.
4	Session with partners. Repetition and deepening of session 3	10	Session with partners. Repetition and deepening of sessions 8 and 9.
5	Handling of outer and inner triggers. The female body and functions of the vulva.	11	Deepening of themes from all sessions. New insights and experiences.
6	Self-touching, masturbation, and orgasm. Steps to overcome hindrances.	12	Further integration of themes. Plans for continued practice at home.

The next critical step in the development of TYSB is to conduct a comprehensive feasibility study. This will assess its potential efficacy and appropriateness for the target group before we can write a final course manual and proceed to a larger Randomized Control Study (RCT).

1.1 Innovations elements and improvements

Despite sexuality being a central aspect of human life and an important health factor, interventions targeting traumatized sexuality are missing in public healthcare. The TYSB intervention emerges thus as a novel contribution to this field, eliciting significant interest from mental health clinics and sexologists both within Norway and internationally.

Traditional trauma treatment has a limited effect on sexual symptoms, which leads to unsatisfactory treatment results and a poorer quality of life for victims of abuse (10, 20) . Furthermore, traumatized sexuality affects partners and the overall dynamics of the relationship, which can further complicate the healing process (9). There is very little research on partners' experiences in the context of treatment for traumatized sexuality, leaving a critical gap in the understanding of how to support both abused women and their partners in recovery. Consequently, there is a critical need for innovative treatment approaches that specifically address rehabilitation of traumatized sexuality, and which take partners and the relational context into account. Furthermore, with many sexually abused women seeking treatment in specialized mental health care, there is a need for efficient and cost-effective group treatment interventions that can accommodate women with a wide range of trauma-related symptoms and sexual problems. The novel TYSB intervention seeks to fill the gap concerning transdiagnostic, group-based approaches that integrate trauma-focused

therapy with a sex-positive framework and include partners in the treatment (20, 23, 25). **There is an urgent requirement to collect in-depth understanding of how participants and their partners experience the TYSB intervention to identify required improvements, investigate the potential efficacy of the intervention and to broaden the research on therapeutic methods for addressing sexual dysfunctions following sexual abuse.**

Trauma patients exhibit a wide range of symptom profiles, making it essential to evaluate appropriate measures for assessing treatment outcomes (26). This heterogeneity is evident in the varying patterns of neural activation observed among patients. Incorporating physiological measurements provides objective indices to investigate treatment responses more accurately (27). **The complexity of trauma-related symptoms cannot be fully captured through quantitative data alone and there is a need to assess a more comprehensive understanding of treatment outcomes (26). Employing a mixed methods design that includes participants' own interpretations and understandings of quantitative results adds significant value and is a novel contribution to the research community (28).** Given the centrality of personal meaning in recovery-oriented practice, our application of a phenomenological perspective in researching this treatment represents a significant innovation (29).

2. Hypotheses, aims and objectives

The overall goal of this project is to ensure the quality of the novel TYSB intervention and lay the ground for a larger-scale RCT of the intervention. The project's overall goal is dispersed into three main aims, each in correspondence with a sub-study (study A, B and C):

Aim 1 (Study A): To investigate the lived experiences of participants in the intervention groups to evaluate the acceptability of the TYSB intervention and identify modifications required to improve the intervention.

Research question (RQ1): What are the participants lived experiences and perceptions of the intervention, and how do they react to any positive or negative impacts attributed to it?

Aim 2 (Study B): To explore the experiences and perspectives of partners of the participants in the intervention groups, with the aim of identifying areas for potential improvement in the intervention and specifically how partners can best be involved in the rehabilitation process.

RQ2: What are the partners' experiences of participating in the intervention and of being witness to and taking part in their partners (participants) process during the intervention?

Aim 3 (Study C): To establish foundational data, methodologies, and effect sizes for a subsequent full-scale RCT.

RQ3: What are the changes in patient-reported levels of PTSD symptoms, sexual satisfaction, sexual shame, interoceptive awareness and reactions to touch from pre intervention to post-intervention and at a 3-month follow-up?

RQ4: How do the capabilities for regulating the autonomic nervous system measured by cardiovascular measurement (ECG) during a script-driven imagery (SDI) procedure change from before to after treatment and at follow-up?

RQ5: What is the adherence rate (recruitment, dropout, and attendance rates among participants) to the intervention?

RQ6: How do the participants interpret and reflect on the quantitative data collected at pre-post intervention and follow-up, with a specific focus on data that stands out or are unexpected in relation to their lived experiences?

Hypothesis (H1): Measurements will show improvements in PTSD symptoms, sexual satisfaction, sexual shame, interoceptive awareness and capability to enjoy touch after the intervention and at follow-up compared to baseline.

H2: Cardiovascular measurement (ECG) during a script-driven imagery (SDI) is a promising method for testing in a RCT.

H3: The study will demonstrate that it is feasible to recruit participants and that at least 80% of them complete the intervention and the study

H4: Participants' reflections will generate new knowledge concerning trauma treatment evaluation identifying relevant primary outcome measures for a larger-scale RCT study.

3. Approach

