3.1. Methods, analyses and technologies

The adoption of a mixed methods design is pivotal for a comprehensive exploration of the feasibility and potential challenges associated with a larger-scale randomized controlled trial (RCT) of the effects of an intervention (28). **Employing multiple perspectives allows for a more complete understanding and facilitates a nuanced assessment of the acceptability of the TYSB intervention.** It is crucial to incorporate the voices of sexually traumatized women and their eventual partners when the research project focuses on a treatment intervention to which they are subjected (29). A mixed methods study employs both qualitative and quantitative methods to collect and analyze data, as well as to organize procedures for investigating research questions. We have described the study design in Figure 1.

Recruitment of participants

To gain access to data that can shed light on the research questions, two groups will be conducted according to the TYSB intervention described above, each consisting of ten women (N=20). We will recruit participants from patients referred to specialized mental health care and the TYSB intervention at STHF. The recruitment process follows standard clinical practice to ensure the selection of appropriate participants for the study. *Inclusion criteria:* a) A history of sexual trauma, b) Experience trauma-related sexual problems, c) Age between 18 and 65 years, d) Enough competence in Norwegian to participate in a psychoeducational group. *Exclusion criteria:* a) Acute suicidality, b) Serious substance abuse interfering with treatment, c) Severe dissociative or psychotic disorders, d) Current life crisis interfering with treatment e) Living in an abusive relationship.

Data collection

Study A and study B: These are qualitative studies where we collect data from exploratory semi-structured in-depth interviews with participants (including possible dropouts) and partners post intervention. We will use interview guides to provide a framework to ensure that all participants are asked about the same core topics.

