Qualitative data analysis (study A, study B and the qualitative part of study C): Qualitative data will be analyzed using Giorgi's descriptive phenomenological method: (1) reading descriptions to grasp the whole, (2) dividing into meaning units, (3) identifying invariant, general meanings in psychological terms, and (4) synthesizing them into a general meaning structure (40). To ensure that the results are reliable, valid and credible, both supervisors will read all the interviews, critically assess the PhD candidate's analysis, and discuss and resolve any discrepancies in interpretation.

Quantitative data analyses (study C):

Quantitative data will be analyzed through linear mixed model analysis (procedure MIXED in SPSS) for statistical comparison of pre-post and follow-up changes in psychometric variables and physiological reactivity. Paired samples t test (two-tailed) will be used for statistical comparison. Due to the small sample size and explorative nature of the study, no statistical correction for multiple testing will be applied. To ensure a 95% confidence interval, analyzes will be performed with a bootstrapping technique. Missing responses will be handled through multiple imputation techniques. Overall significance level set at .05.

Figure 1: The projects study design

The doctoral thesis will utilize collected data and results to draw comprehensive conclusions about the TYSB interventions overall feasibility and associated risks and complications. These conclusions will inform the design of a future RCT, including power calculations, as well as primary outcomes, generating hypotheses, and providing insights into necessary modifications to optimize the TYSB intervention and its protocol, thereby improving validity and reliability.

Potential weaknesses and risks

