We recognize the potential risk of participant drop-out. To ensure enough participants there will be conducted an interim analysis post intervention. A third group will be included in autumn 2026 if there is a larger dropout of women (>3) or less partners (<10) than expected or if the interim analysis reveals that a larger N is needed for designing an adequately powered future study. A potential source of bias in this study stems from the dual role of the PhD candidate, who is also developer of the treatment intervention. This overlap can introduce bias, affecting the impartiality of the study. To mitigate these risks, several strategies have been implemented: Independent therapists conduct the intervention groups, eliminating direct involvement from the researcher. In *studies A* and *B*, interviews are conducted by a co-researcher and user participant unconnected to the intervention, safeguarding impartial data collection and encouraging honest feedback. The analysis of the qualitative data will be done by the PhD candidate in close collaboration with the main supervisor and the co-supervisor who have no connection to the development of the

intervention and no financial interests in the project. It is considered that the PhD candidate's in-depth knowledge of both the intervention and the topic will strengthen the quality of the analysis. The independent supervisors will thoroughly review all interviews, offering new perspectives and critical reflections. They will validate and challenge methodological choices throughout the entire process to ensure that the results are reliable, valid, and credible. Statistical analyzes of the quantitative data will be carried out by the main supervisor in collaboration with an independent statistician at STHF, who has no connection to the intervention. Quantitative data from the questionnaires will be compared with objective physiological measures and participants own understanding of the results. This triangulation of data sources helps to strengthen the dataset and offers a more robust and unbiased objective assessment of the feasibility and acceptability of the intervention. Collectively, these strategies are essential for ensuring the study's reliability and reducing the likelihood that results will be influenced by the researcher's personal interests or expectations.

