3.4 Plan for activities, visibility and dissemination

Activity	From	To
Approval PVO/REK. Planning, recruitment and implementation of study group 1. Pre- and post-test QUAN data collection. Recruitment of participants (group 2).	Jan 2025	Dec 2025
Study group 1: QUAL data collection for study A and study B	Jan 2026	Feb 2025
Study group 2: Pre-test QUAN data collection, post-test QUAN data collection and QUAL data collection for study A and study B.	Feb 2026	May 2026

Study group 1: Follow-up QUAN data collection, analyzing pre-post and follow-up QUAN data and collecting QUAL data for study C.	Apr 2026	Apr 2026
Study group 2: Follow-up QUAN data collection, analyzing pre-post and follow-up QUAN data and collecting QUAL data for study C.	Aug 2026	Aug 2026
Analysis of data study A and complete article study A.	Feb 2026	Feb 2027
Analysis of data study B and complete article study B. Presenting at a conference.	Jul 2026	Sep 2027
Analysis of data study C and complete article study C.	Jan 2027	Feb 2028
Complete mantle. Dissemination of the project at conferences and open lectures.	Oct 2027	Dec 2028

Plan for dissemination of results

We will disseminate the findings from this study through three scientific articles and presentations at scientific conferences. Potential titles of articles:

Study A: *Voices of transformation: A deep dive into the struggles and successes of reclaiming sexuality after sexual trauma.*

Study B: *Healing together: partners' experiences in the journey of sexual trauma recovery through the intervention Take your sexuality back for sexually traumatized women.*

Study C: *A feasibility mixed methods study of the intervention Take your sexuality back for sexually traumatized women: Preliminary evaluations of efficacy and outcome measurements.*

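### Aim 3 promises effect sizes for the RCT, but on the outcome measures Study C yields only uncontrolled change from baseline, and the protocol does not list this as a limitation

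*Protocol*

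**What the plan says.** Section 2 gives Study C the aim "To establish foundational data, methodologies, and effect sizes for a subsequent full-scale RCT". Section 3.1, at the end of the data analysis part, says of the project's overall conclusions: "These conclusions will inform the design of a future RCT, including power calculations".

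The design is in section 3.1 under recruitment: "two groups will be conducted according to the TYSB intervention described above, each consisting of ten women (N=20". Both groups receive the intervention, and no comparator is described. Under section 6, women who decline the study can still have the same treatment, so they are not an untreated comparison either.

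The outcome questions are about change over time. RQ3 and RQ4 ask about change from before treatment, H1 predicts improvement "after the intervention and at follow-up compared to baseline", and the analysis is a "statistical comparison of pre-post and follow-up changes in psychometric variables and physiological reactivity" by mixed model and paired t test. Study C also covers recruitment, dropout and attendance (RQ5) and at least 80% completion (H3).

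The part of section 3.1 on weaknesses and risks deals with dropout and with the developer's involvement: "A potential source of bias in this study stems from the dual role of the PhD candidate". It also allows a third group "if the interim analysis reveals that a larger N is needed for designing an adequately powered future study". The missing control group is not mentioned there.

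**The concern.** A parallel-group RCT is powered on the difference between arms. On the outcome measures, Study C estimates how much treated women change. The two agree only if women in the RCT's control arm would not change at all.

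Several things other than the intervention could move the scores: the natural course of symptoms, answering the same forms three times, and contact with a therapist outside the group (section 6). Regression to the mean is possible because the women are referred patients, but the inclusion criteria set no severity cut-off, so this is less certain.

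Preparing the RCT is the project's stated overall goal. If the later trial took the uncontrolled change as its expected effect and its controls also improved, it would be too small. The harm would fall on that trial, not on the women or analyses in this one.

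**Working it through.** **No figure to reproduce.** The protocol gives no effect size, SD, power or sample-size calculation; 20 is two groups of ten.

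**Inputs from the protocol.** One treated group, N = 20; comparisons with baseline; two-sided 0.05 (all section 3.1).

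**Assumed inputs, for illustration.** RCT power 80%, equal arms, SD 1, standardised pre-post change d = 0.5, control-arm change c from 0 to 0.3 SD, pre-post correlation r from 0.3 to 0.7.

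**1. What is estimated.** Let τ be the effect of the intervention against the RCT's comparator and c the change under that comparator.
- Mean change in Study C: τ + c.
- RCT effect: (τ + c) − c = τ.
- The gap is c, whatever the number of women. The protocol does not name the RCT's comparator, so c is unknown.

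**2. RCT sized on the uncontrolled change.** By normal approximation, n per arm = 2(1.960 + 0.842)²/d² = 2 × 7.85/0.25 = 62.8, so 63. The noncentral t gives 64.

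**3. Power with 64 per arm when the true effect is 0.5 − c.** Noncentrality = (0.5 − c) × √(64/2) = (0.5 − c) × 5.657, with 126 degrees of freedom.

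| c (SD) | true effect | noncentrality | power | n per arm for 80% |
|---|---|---|---|---|
| 0 | 0.50 | 2.83 | 80% | 64 |
| 0.05 | 0.45 | 2.55 | 71% | 79 |
| 0.1 | 0.40 | 2.26 | 61% | 100 |
| 0.2 | 0.30 | 1.70 | 39% | 176 |
| 0.3 | 0.20 | 1.13 | 20% | 394 |

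**4. If the RCT is sized without baseline adjustment but analysed with it.** The residual SD is multiplied by √(1 − r²), which is 0.866 at r = 0.5. To vary r, the paired effect dz is held at 0.5 and d = dz√(2(1 − r)), giving d = 0.59, 0.50 and 0.39.

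| r | n per arm | unadjusted power at c = 0.05 / 0.1 / 0.2 / 0.3 | adjusted power at the same c |
|---|---|---|---|
| 0.3 | 46 | 73 / 65 / 46 / 28% | 77 / 69 / 50 / 31% |
| 0.5 | 64 | 71 / 61 / 39 / 20% | 83 / 74 / 49 / 25% |
| 0.7 | 106 | 69 / 55 / 27 / 10% | 93 / 83 / 48 / 14% |

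With adjustment the shortfall is small or absent at c = 0.05, and absent at c = 0.1 when r = 0.7. It is large in every row at c = 0.2 or more.

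**5. What a third group would do.** Assuming ten more women, the 95% CI for an observed dz of 0.5 narrows from 0.03–0.96 (n = 20) to 0.12–0.88 (n = 30). The gap c from step 1 stays the same.

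**6. What one arm can supply.** The 95% CI for an SD, as a multiple of the estimate, is √((n − 1)/χ²). This gives 0.76 to 1.46 at n = 20 and 0.80 to 1.34 at n = 30. RCT size goes with the SD squared, so at n = 20 it could range from 0.58 to 2.13 times the planned value.

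**The case against.** The strongest reply is that the protocol nowhere says pre-post change will be used as the RCT effect. A reader might infer that plan from Aim 3, but the text does not support it. The sentence on power in section 3.1 refers to conclusions drawn from all the data, and SDs, correlations, dropout and attendance are proper inputs to a power calculation. RQ3, RQ4 and H1 openly describe change from before treatment, so the quantity is not mislabelled there. This stands, and it makes the harm conditional.

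A reader might also infer that Study C can tell the RCT nothing but uncontrolled change, or that it needs a control arm. Neither follows. It also measures recruitment, attendance and completion, and a feasibility study may have one arm.

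The figures above are assumed, and sections 1 and 1.1 report little effect of traditional trauma treatment on sexual problems. Small control change is therefore the more plausible case for the sexual outcomes. That argument does not extend to PTSD symptoms.

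Finally, the protocol is cautious in tone: it calls the study explorative, and the proposed Study C title has "Preliminary evaluations of efficacy and outcome measurements". But the first remark serves only to justify omitting a multiplicity correction, and neither mentions the missing control. What remains is that effect sizes for the RCT are a named product, the only outcome effects available are uncontrolled, and the stated weaknesses omit this.

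**Conclusion.** The point holds as a matter of wording and stated limitations. On the outcome measures, Study C cannot provide the between-group effect size that Aim 3 appears to promise, and the protocol should say so. That conclusion follows from the design alone.

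Its size depends on assumptions. With d = 0.5 and an unadjusted RCT of 64 per arm, power runs from 80% with no control change to 20% at 0.3 SD. Adjustment for baseline removes most or all of the loss when control change is small. The third-group rule is not wrong for this reason: more women would sharpen the estimates, but would not turn them into a between-group effect. Figure 1 could not be seen in the text available. Severity: minor.

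**What to change.** - **Aim 3 (section 2) and the closing paragraph on data analysis (section 3.1):** say that Study C supplies pre-post and follow-up change, labelled as uncontrolled, together with outcome SDs, pre-post correlations, recruitment, attendance and completion, each with a 95% CI.
- **Same place:** state that the observed change will not be taken as the RCT's between-group effect, and that the target difference will be justified separately.
- **Weaknesses and risks (section 3.1):** add the missing control group, and note that a third group would improve precision without removing this limitation.

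The cost is a few sentences, with no new measurements and no extra women. The study gives up the claim to deliver an RCT effect size, and the team must justify a target difference from elsewhere. The SDs it supplies will still be imprecise, which the reported intervals will make visible.
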